# 10 STATISTICAL CONSIDERATIONS

## 10.1 SAMPLE SIZE/ACCRUAL RATE

The primary objective of this trial is to determine whether use of CRd is associated with a substantial fraction of patients with high-risk SMM who exhibit at least a VGPR from baseline until the end of 8 cycles of treatment.

The study will initially enroll 12 evaluable patients and determine M-spike levels on each patient pre-treatment as well as after each cycle of treatment. The percent decline from baseline will be determined for each patient. If 12 evaluable patients are enrolled and if 5 or more patients exhibit a VGPR, then the probability of this occurring is 7.3% if the true probability of a VGPR decline is 20%. The probability of 5 or more with a 50% decline is 80.6% if the true probability of a VGPR decline is 50%. Thus, obtaining 5 or more patients out of 12 with a VGPR would provide strong evidence that the true probability of a VGPR was consistent with 50% or more as opposed to 20%.

Version Date: 01/01/2024

In order to allow for a small number of inevaluable patients, the initial accrual ceiling will be set at 14.

If 1-2 patients per month can be enrolled on this trial, it expected that accrual could be completed in 6 to 12 months.

Amendment C (version date 07/11/2013) will permit enrollment to a replicate cohort in order to more precisely define the response rate to the CRd regimen in this population. Based on preliminary results from the first 8 evaluable patients on the initial pilot cohort, 7 patients have experienced a VGPR or better response (87.5%). Amendment C (version date 07/11/2013) will allow enrollment of a replicate cohort of 16 evaluable patients in order to estimate the response rate in this cohort independently from the initial cohort of 12 evaluable patients. With 16 evaluable patients, a two-sided 90% confidence interval for the proportion of patients with a VGPR or greater will extend +/- 14% from the observed proportion if the expected proportion is 87%.

Thus, 16 newly enrolled patients will be evaluated for response separately from the initial 12 patients. If the proportions with a VGPR are sufficiently similar (approximately p>0.35 by a Fisher's exact test), then in addition to reporting the results separately, an additional result will be the combined proportion of VGPR or greater along with a two-sided 90% confidence interval about this observed proportion. If there are 28 total patients which can be combined in an evaluation, a simple two-sided 90% confidence interval for the proportion of patients with VGPR or greater will extend approximately +/- 11% from the observed proportion if the expected proportion is 86% (24 of 28 responses, for example).

Enrolling additional patients to this replicate cohort will allow the secondary endpoints of duration of response and PFS to be determined with greater precision; it will also allow us to conduct stratified analysis by molecular subtypes (hyperdiploid vs. non-hyperdiploid); and it will provide greater safety data than that available from the pilot cohort of 12 patients.

All 18 patients enrolled on the trial during 2012-2014 exhibited VGPR or better responses, including 17 with some variation of a CR and 16 who were MRD(-). Beginning with Amendment L (version date 05/17/2018), the primary objective of the trial is revised to increase the precision of the estimate of the MRD (-) CR rate. The trial will be extended to enroll a total of 50 evaluable patients to do so. With a total of 50 evaluable patients, the 95% two-sided confidence interval width about a conservative estimate of the MRD (-) CR rate of 70% would be +/- 12.7%. If the MRD (-) CR rate were 85%, 50 patients would permit the estimate to be determined with a 95% two-sided confidence interval of +/- 9.9%.

As of January 2018, a total of 21 patients have been enrolled on the trial and it is anticipated that 1-2 patients per month will continue to be accrued. Thus, it is expected that the remaining 29 patients can be enrolled in approximately 2 years. To allow for a number of inevaluable patients and screen failures, the accrual ceiling will be set at 63.

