## 10.2 STATISTICAL ANALYSIS OF SECONDARY/EXPLORATORY ENDPOINTS

Secondary endpoints are duration of response and progression free survival (both biochemical progression and progression to overt symptomatic multiple myeloma). Duration of response is defined as time from response to disease progression or death. Progression free survival is defined as time of study entry to progression or death. Duration of response and progression free

*Version Date:* 01/01/2024

survival will be estimated using the Kaplan-Meier and log-rank methods. Secondary endpoints will also include rate and duration of MRD-negative CR and OS.

A number of correlative studies will be performed in order to assess carfilzomib in vitro biological activity and investigate minimal residual disease in SMM. Minimal residual disease will be further explored using multi-parametric flow cytometry, PCR-based techniques, and advanced imaging.

Beginning with Amendment L (version date 05/17/2018), the secondary objectives will also include:

- 1. To estimate the durable MRD (-) CR rate, estimating the fraction of patients who have an MRD (-) CR for 1 year as a minimum. This fraction will be estimated along with a 95% two-sided confidence interval.
- 2. To compare the outcomes among the 18 patients enrolled in 2014 or earlier to the 32 enrolled in 2017 or later because the diagnostic criteria for SMM vs. MM were revised in 2014 after the 18th patient was enrolled. The MRD (-) CR rates will be compared between these two cohorts of patients using a two-tailed Fisher's exact test. All other comparisons of outcomes between the two cohorts will be interpreted as exploratory and will be done using appropriate non-parametric statistical tests without adjustment for multiple comparisons.
- 3. To obtain and report safety data on all enrolled evaluable patients to fully characterize the safety of the regimen in a modestly large number of subjects treated on one protocol.

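### Section 10.1 reports a combined VGPR rate only if a small Fisher test finds no difference between 12 and 16 patients; given the 18/18 result, the rule can now withhold only the less favourable totals

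*Combined protocol and SAP*

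**What the plan says.** Section 10.1 sets up a replicate cohort under Amendment C: "16 newly enrolled patients will be evaluated for response separately from the initial 12 patients". Whether the two proportions are close enough is judged by the criterion "approximately p>0.35 by a Fisher's exact test". The consequence of meeting it is worded as follows: "then in addition to reporting the results separately, an additional result will be the combined proportion of VGPR or greater", with a two-sided 90% CI. The separate results are therefore always reported, and the test controls only the extra combined line.

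The precision statements are that the interval for 16 patients "will extend +/- 14% from the observed proportion if the expected proportion is 87" per cent, and that the interval for 28 patients "will extend approximately +/- 11% from the observed proportion if the expected proportion is 86% (24 of 28 responses, for example").

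The same section later states: "All 18 patients enrolled on the trial during 2012-2014 exhibited VGPR or better responses". From Amendment L the primary objective becomes the MRD(-) CR rate in 50 evaluable patients, with no pooling condition. Section 10.2 compares "the 18 patients enrolled in 2014 or earlier to the 32 enrolled in 2017 or later", because the diagnostic criteria were revised in 2014 after the 18th patient.

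The pooling rule is current text. Section 1.1.2 marks one dropped objective as no longer applying; nothing similar is attached to this rule, and Section 10.1 still opens with a VGPR-based primary objective.

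**The concern.** Three features deserve attention.

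- A non-significant Fisher test with 12 and 16 patients says little about whether two response rates are alike. A threshold of 0.35 instead of 0.05 makes the screen stricter but does not turn it into a test of similarity.
- Whether the combined figure appears depends on the data. Once the first cohort sits at its ceiling, the only way to fail is for the replicate to look worse, so the combined figure is missing when it would be less favourable.
- The boundary at patient 12 is not where the trial population is documented to have changed. That is at patient 18.

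At stake is how the overall VGPR-or-better rate reads in the final report, and whether its 90% CI, computed as if no condition existed, describes what was done.

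**Working it through.** **Inputs.** Cohorts of 12 and 16, the p>0.35 rule, expected rates of 86-87% and the 18/18 result are from Section 10.1. The change after patient 18 is from Section 10.2. Section 3.1.2 gives 18 patients enrolled at closure and 10-12 remaining.

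**Assumptions.** Evaluable patients fill the cohorts in enrolment order, all 18 early patients are evaluable, and the test is two-sided. Section 10.1 does not state the sidedness.

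**1. The plan's own figures.** Half-width = 1.645 × √(p(1−p)/n).
- n=16, p=0.87: 1.645 × √(0.87×0.13/16) = 13.8%. Stated: 14%.
- n=28, p=0.86: 1.645 × √(0.86×0.14/28) = 10.8%. Stated: about 11%.

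Both reproduce. The plan gives no operating characteristics for the pooling rule.

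**2. The rule before any data.** Compute the two-sided Fisher p for every pair of outcomes (a/12, b/16), and weight each pair by Binomial(12, p1) × Binomial(16, p2).

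| True rates | Combined rate reported | Mean combined rate when reported | Mean without the condition |
|---|---|---|---|
| 87% / 87% | 81% | 87.2% | 87.0% |
| 87% / 75% | 68% | 80.7% | 80.1% |
| 87% / 70% | 58% | 78.2% | 77.3% |

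At 87%/87% the rule refuses 19.0% of the time: 8.2 points because the replicate looks worse and 10.9 because it looks better (rounded). With 10/12 in the first cohort, for example, a replicate of 16/16 is not pooled (p=0.175). The bias is under 1 point in all three rows.

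**3. The rule given 18/18.** The first cohort is 12/12, so every non-responder is in the replicate. With m non-responders among 28, the two-sided p adds the two extreme tables: p = [C(16,m) + C(12,m)] / C(28,m) for m = 2, 3, 4.
- m=4 (12/16): (1820 + 495)/20475 = 0.113, not pooled.
- m=3 (13/16): (560 + 220)/3276 = 0.238, not pooled.
- m=2 (14/16): (120 + 66)/378 = 0.492, pooled.

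At 15/16 and 16/16, p=1. The combined rate can therefore be only 26/28, 27/28 or 28/28, that is, at least 92.9%. The plan's illustrative 24/28 would now have to be 12/12 plus 12/16, and would be withheld.

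**4. Size of the selection effect.** The same 18/18 fixes patients 13-18 at 6/6, so only 10 replicate patients (19-28) are random. Pooling needs at least 8 of these 10. With Y ~ Binomial(10, p), compare E[(18+Y)/28 | Y≥8] with (18+10p)/28.

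| True rate in the 10 later patients (assumed) | Combined rate reported | Mean when reported | Mean without the condition | Difference |
|---|---|---|---|---|
| 87% | 87% | 96.4% | 95.4% | 1.0 |
| 75% | 53% | 94.9% | 91.1% | 3.8 |
| 60% | 17% | 94.0% | 85.7% | 8.3 |

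**5. The boundary.** Patients 13-28 comprise 6 enrolled in 2014 or earlier and 10 enrolled later. Suppose 8 of those 10 respond. The rule as written compares 12/12 with 14/16 (p=0.492) and pools. The same threshold at the criteria change compares 18/18 with 8/10 (p=0.119) and would not pool. The current split dilutes the contrast that Section 10.2 identifies.

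**The case against.** The strongest reply has four parts, and most of it stands.

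- **Little is hidden.** Both cohort proportions are reported whatever the test shows, and a reader can add them.
- **The rule was even-handed when introduced.** Amendment C cites 7 of 8 responders, not 12 of 12. At 87%/87% more of the refusals come from a replicate that looks better than from one that looks worse.
- **VGPR is no longer the primary target.** The MRD(-) CR estimate in 50 patients does not pass through this rule.
- **The relevant comparison is already allowed.** Section 10.2 permits exploratory comparisons of other outcomes at 18 versus 32, which can include VGPR.

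A reader might go further and infer that the rule was built to suppress an unfavourable pooled estimate, or that it is biased upward in general. The documents do not support this: the rule is two-directional, and its bias before data is under 1 point at the rates examined. The one-sided behaviour comes from the observed 18/18.

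A reader might also condition only on 12/12, treat all 16 replicate patients as unknown at 75%, and obtain 94.2% against 85.7%. That uses half of the 18/18 statement. With patients 13-18 fixed at 6/6 as well, the gap at 75% falls from 8.5 to 3.8 points.

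The reply does not remove the condition from current text, supply an unconditional overall VGPR rate, or align the 12/16 split with the criteria change.

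**Conclusion.** The point holds as a low-priority improvement. Given 18/18, the rule can fail only downward and shows a combined rate only at 26/28 or more. The resulting upward selection is about 1 point if the 10 later patients respond at the planned 87%, 3.8 points at 75% and 8.3 points at 60%. The last two rates are assumptions chosen to show the range; the plan itself expects 86-87%.

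These figures rest on enrolment order, evaluability of all 18 early patients and a two-sided test. If the test were one-sided, 14/16 would give 120/378 = 0.317 and would also be withheld, so the two-sided reading is the more lenient one here.

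It might be inferred that the 90% CI for the combined rate is invalid. The supportable statement is narrower: the interval ignores the selection step. Its actual coverage was not calculated. No current primary conclusion depends on this rule.

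**What to change.** In Section 10.1, delete the p>0.35 condition. Always report the overall VGPR-or-better rate with an exact two-sided 90% CI, and state its denominator. Beside it give the separate cohort rates (12 and 16) and the rates split at the 2014 criteria change (18 versus 32), the boundary already used in Section 10.2. Any difference can then be described there without deciding what is shown.

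The cost is about one sentence in 10.1, with no new patients, visits or assays. The drawback is that the combined figure may be less favourable. The study calendar notes that all participants had completed maintenance by February 2023, so the amendment should record that the change was made after induction responses were available.

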#### 5 CORRELATIVE STUDIES FOR RESEARCH

#### 5.1 BIOSPECIMEN COLLECTION

	Baseline	During Cycle 2-8 or End of Cycle 8*	During Extended Dosing Phases of Cycles 9-20/ End of Cycle 20 OR Cycles 21-32/End of Cycle 32/ End of Treatment#	Follow-Up Period after 32 cycles of maintenance every 3-6 months^	Disease Progression
Pathology/IHC	X	X	X	X	X
Multiparametric Flow Cytometry	X	X	X	X	X
FISH/Cytogenetics	X				X
Molecular pathology for light or heavy chain immunoglobulin rearrangement and/or KRas and NRas mutation analysis (NOTE: Not to be performed as of Amendment H (version date 06/30/2017))	X	X (optional)	X (optional)		X
CD138+ sorting/Gene expression profiling/microenvironment	X	X	X	X	X
Other research lab as below, including Next Generation Sequencing	X	X	X	X	X
Storage	X	X	X	X	X

\*During Cycle 2-8 if CR achieved or End of Cycle 8 if no CR is achieved

Note: Biospecimen collection directly from participants is completed; analyses are undergoing.

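### Do the symmetric precision figures for 50 patients, and the lack of a named interval method, weaken the estimate of the MRD(-) CR rate?

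*Combined protocol and SAP*

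**What the plan says.** Since Amendment L, section 10.1 states that "the primary objective of the trial is revised to increase the precision of the estimate of the MRD (-) CR rate", with a total of 50 evaluable patients. The numerical support is a 95% two-sided interval whose width "about a conservative estimate of the MRD (-) CR rate of 70% would be +/- 12.7" points; for a rate of 85%, "50 patients would permit the estimate to be determined with a 95% two-sided confidence interval of +/- 9.9" points. No hypothesis test, null rate or success rule is attached to this endpoint.

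For the durable MRD(-) CR rate (at least one year), section 10.2 says "This fraction will be estimated along with a 95% two-sided confidence interval". It does not name the method.

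The nearest wording to a method belongs to the VGPR endpoint that preceded Amendment L. For the two early cohorts combined (28 patients), section 10.1 says that "a simple two-sided 90% confidence interval for the proportion of patients with VGPR or greater will extend approximately +/- 11" points at 86%, and that "an additional result will be the combined proportion of VGPR or greater along with a two-sided 90% confidence interval about this observed proportion". Section 10.1 also records that "All 18 patients enrolled on the trial during 2012-2014 exhibited VGPR or better responses", 16 of them MRD(-).

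**The concern.** With no decision rule, the confidence interval is the main inferential result for the MRD(-) CR rate. Three features draw attention.

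- The precision is given as a symmetric plus-or-minus figure. At rates of 70% to 85% with 50 patients, a score or exact interval reaches further below the estimate than above it. A reader who takes the stated figure literally expects a lower limit that is too high.
- No method is named for the final intervals, so the choice could in principle be made after the data are seen.
- If the planning formula were carried into the analysis, coverage would fall below 95%, with most misses on the optimistic side. At 100% response it would give an interval of zero width, and VGPR or better has already been seen in 18 of 18 patients.

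At stake would be a lower limit that flatters the regimen in an open-label, single-arm trial.

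**Working it through.** **Inputs.** n = 50, 95% two-sided (z = 1.96), rates 70% and 85%, all from section 10.1.

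**1. Reproduce the plan's figures.** Wald half-width = z × √(p(1−p)/n).

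- 70%: 1.96 × √(0.70 × 0.30 / 50) = 0.127
- 85%: 1.96 × √(0.85 × 0.15 / 50) = 0.099

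Both match. The 90% VGPR figures follow the same formula (z = 1.645):

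- n = 16, 87%: 1.645 × √(0.87 × 0.13 / 16) = 0.138 (stated 14)
- n = 28, 86%: 1.645 × √(0.86 × 0.14 / 28) = 0.108 (stated 11)

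**2. Is the planned width right?** Wilson half-width = z × √(p(1−p)/n + z²/(4n²)) / (1 + z²/n), with z² = 3.8415.

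- 70%: 1.96 × √(0.0042 + 0.000384) / 1.0768 = 0.123
- 85%: 1.96 × √(0.00255 + 0.000384) / 1.0768 = 0.0986

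The stated 12.7 and 9.9 compare with Wilson values of 12.3 and 9.86. The average Clopper-Pearson half-width is 13.4 at 35/50, 11.0 at 42/50 and 10.5 at 43/50. The planned precision is therefore close to Wilson and up to about 1 point tighter than the conservative exact interval.

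**3. How far do the limits move?** A rate of 85% would need 42.5 responders, so the neighbouring counts are shown (95% limits, %).

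| Responders | Wald | Wilson | Clopper-Pearson |
|---|---|---|---|
| 35/50 (70%) | 57.3–82.7 | 56.2–80.9 | 55.4–82.1 |
| 42/50 (84%) | 73.8–94.2 | 71.5–91.7 | 70.9–92.8 |
| 43/50 (86%) | 76.4–95.6 | 73.8–93.0 | 73.3–94.2 |

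At the same count:

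- The Wald lower limit is higher than Wilson / Clopper-Pearson by 1.1 / 1.9 points (35/50), 2.4 / 3.0 (42/50) and 2.6 / 3.1 (43/50).
- The Wald upper limit is higher by 1.8 / 0.6, 2.5 / 1.3 and 2.6 / 1.4 points.
- The Wilson and Clopper-Pearson lower limits differ from each other by less than 1 point at all three counts.

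**4. Coverage, only if Wald were used for the final interval.** Summing the binomial probabilities over all 51 possible counts at n = 50:

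| True rate | Wald | Wilson | Clopper-Pearson |
|---|---|---|---|
| 70% | 93.5% | 95.7% | 97.0% |
| 85% | 94.1% | 95.6% | 97.3% |

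At the plan's two rates the Wald shortfall is 1.5 and 0.9 points. The share of Wald intervals lying wholly above the true rate is 4.0% and 4.6%, against a nominal 2.5%.

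**5. The 18/18 case.** The VGPR intervals in section 10.1 are for the 16-patient replicate cohort and the 28 patients combined. None is planned for the 18 enrolled in 2012–2014. If those 18 count among the 28, a zero-width combined interval would also need the other 28 − 18 = 10 patients to reach VGPR.

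**The case for a change.** The strongest case for a change is that these intervals are the trial's main statistical result and that naming a method costs one sentence. The plan does name methods elsewhere (Fisher's exact test, Kaplan-Meier). The only interval form visible in the text is plus-or-minus around the observed proportion, and for the 16-patient cohort that form already exceeds the possible range: 87 + 14 = 101%. The first 18 patients gave 16/18 = 88.9% MRD(-), and Wald does worse at such rates: at n = 50 its coverage is 91.7% at a true 89% and 87.9% at a true 90%. The error favours the regimen.

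Much of this is correct as description. The method is unnamed, Wald would be a poor choice near 90%, and a sentence fixing Wilson or Clopper-Pearson would be tidy.

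It does not amount to a fault, for four reasons. The coverage loss needs a step the plan does not take, namely Wald for the final MRD(-) CR interval. The word "simple" belongs to the combined VGPR interval, and the 101% is a planning illustration for an endpoint that Amendment L replaced as the focus. The rate near 89% comes from the earlier cohort, which section 10.2 itself treats as possibly different because the diagnostic criteria were revised in 2014. Finally, fixing the method now would protect little against a data-driven choice: the trial is open-label, and results for 18 of the planned 50 patients are printed in the protocol. The note in section 5.1 that "Biospecimen collection directly from participants is completed; analyses are undergoing" concerns the correlative specimens and does not show where the response-rate analysis stands.

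**Conclusion.** No change to the plan is needed. The 12.7 and 9.9 points are correctly computed planning half-widths of about the right size, and 50 patients remains justified on them. The real gap is an unnamed interval method for the MRD(-) CR and durable MRD(-) CR rates. Any standard choice leaves the point estimate as it is and moves a 95% limit by about 1 to 3 points at the expected counts, with no decision attached to either limit.

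This rests on two assumptions: that the final rate lies roughly in the range the plan considers (70% to 85%), and that the analyst uses an ordinary binomial interval suited to high proportions and reports which one. If Wald were used and the true rate were near 90%, the lower limit would be noticeably optimistic. A reader could see this and recompute the interval from the reported count and denominator.

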## 10.2 STATISTICAL ANALYSIS OF SECONDARY/EXPLORATORY ENDPOINTS

Secondary endpoints are duration of response and progression free survival (both biochemical progression and progression to overt symptomatic multiple myeloma). Duration of response is defined as time from response to disease progression or death. Progression free survival is defined as time of study entry to progression or death. Duration of response and progression free

*Version Date:* 01/01/2024

survival will be estimated using the Kaplan-Meier and log-rank methods. Secondary endpoints will also include rate and duration of MRD-negative CR and OS.

A number of correlative studies will be performed in order to assess carfilzomib in vitro biological activity and investigate minimal residual disease in SMM. Minimal residual disease will be further explored using multi-parametric flow cytometry, PCR-based techniques, and advanced imaging.

Beginning with Amendment L (version date 05/17/2018), the secondary objectives will also include:

- 1. To estimate the durable MRD (-) CR rate, estimating the fraction of patients who have an MRD (-) CR for 1 year as a minimum. This fraction will be estimated along with a 95% two-sided confidence interval.
- 2. To compare the outcomes among the 18 patients enrolled in 2014 or earlier to the 32 enrolled in 2017 or later because the diagnostic criteria for SMM vs. MM were revised in 2014 after the 18th patient was enrolled. The MRD (-) CR rates will be compared between these two cohorts of patients using a two-tailed Fisher's exact test. All other comparisons of outcomes between the two cohorts will be interpreted as exploratory and will be done using appropriate non-parametric statistical tests without adjustment for multiple comparisons.
- 3. To obtain and report safety data on all enrolled evaluable patients to fully characterize the safety of the regimen in a modestly large number of subjects treated on one protocol.

An exploratory objective is also added to evaluate FISH data on available patients enrolled following amendment L (version date 05/17/2018) with respect to classification into high risk vs. non-high-risk patients. Known high risk FISH markers in multiple myeloma literature will be evaluated, namely, 4;14, 14;16, 14;20, del 17p, and 8;14. When available outside lab results will be confirmed either by results from the NCI Laboratory of Pathology or by the Mayo Laboratory results (Test ID: PCPDF, Plasma Cell Proliferative Disorder (PCPD)) and mutual results will be used for the analysis.

